5.3.2 Exclusion Criteria (applicable to all subjects, including all expansion cohorts)

Subjects are not eligible for this trial if they fulfill any of the following exclusion criteria:

1. Concurrent treatment with a non-permitted drug (see Section [6.5.2](#)).
2. Prior therapy with any antibody/drug targeting T cell co-regulatory proteins (immune checkpoints) such as anti-programmed death 1 (PD-1), anti-PD-L1, or CTLA-4 antibody. For subjects with metastatic melanoma, prior treatment with a CTLA-4 antibody is not an exclusion.
3. Concurrent anticancer treatment within 28 days before the start of trial treatment (e.g., cytoreductive therapy, radiotherapy [with the exception of palliative bone directed radiotherapy], immune therapy, or cytokine therapy except for erythropoietin); major surgery within 28 days before the start of trial treatment (excluding prior diagnostic biopsy); use of hormonal agents within 7 days before the start of trial treatment, except for subjects in the CRPC cohort who may remain on treatment with luteinizing hormone-releasing hormone agonists or antagonists; or use of any investigational drug within 28 days before the start of trial treatment. Subjects in the gastric and GEJ cohort who have not progressed on first-line chemotherapy may be enrolled within the 28-day period following prior treatment provided all toxicity from prior therapy has resolved to Grade ≤ 1 .

Subjects receiving immunosuppressive agents (such as steroids) for any reason should be tapered off these drugs before initiation of the study treatment (with the exception of patients with adrenal insufficiency, who may continue corticosteroids at physiologic replacement dose, equivalent to ≤ 10 mg prednisone daily). Steroids with no or minimal systemic effect (topical, inhalation) are allowed.

4. Previous malignant disease other than the target malignancy to be investigated in this trial within the last 5 years with the exception of basal or squamous cell carcinoma of the skin or cervical carcinoma in situ.
5. Rapidly progressive disease (e.g., tumor lysis syndrome).
6. Active or history of CNS metastases.
7. Receipt of any organ transplantation including allogeneic stem-cell transplantation.
8. Significant acute or chronic infections including, among others:

- Known history of testing positive test for human immunodeficiency virus (HIV) or known acquired immunodeficiency syndrome (AIDS)
 - Positive test for HBV surface antigen and / or confirmatory HCV RNA (if anti-HCV antibody tested positive).
9. Active or history of any autoimmune disease (subjects with diabetes Type I, vitiligo, psoriasis, hypo- or hyperthyroid disease not requiring immunosuppressive treatment are eligible) or immunodeficiencies.
 10. Known severe hypersensitivity reactions to monoclonal antibodies (Grade \geq 3 NCI-CTCAE v4.0), any history of anaphylaxis, or uncontrolled asthma (i.e., 3 or more features of partly controlled asthma) (71).
 11. Persisting toxicity related to prior therapy $>$ Grade 1 NCI-CTCAE v4.0, however sensory neuropathy \leq Grade 2 is acceptable.
 12. Pregnancy or lactation period. Note: a negative pregnancy test is required for women of childbearing potential. Women who are postmenopausal (age-related amenorrhea \geq 12 consecutive months or follicle-stimulating hormone (FSH) $>$ 40 milli international units per milliliter [mIU/mL]), or who had undergone hysterectomy or bilateral oophorectomy are exempt from pregnancy testing. If necessary to confirm postmenopausal status a FSH level will be included at screening.
 13. Known alcohol or drug abuse.
 14. Clinically significant (i.e., active) cardiovascular disease: cerebral vascular accident/stroke ($<$ 6 months prior to enrollment), myocardial infarction ($<$ 6 months prior to enrollment), unstable angina, congestive heart failure (New York Heart Association Classification Class \geq II), or serious uncontrolled cardiac arrhythmia requiring medication.
 15. All other significant diseases (e.g., inflammatory bowel disease), which, in the opinion of the investigator, might impair the subject's tolerance of trial treatment.
 16. Any psychiatric condition that would prohibit the understanding or rendering of informed consent.
 17. Legal incapacity or limited legal capacity.
 18. Vaccination within 4 weeks of the first dose of avelumab and while on study is prohibited except for administration of inactivated vaccines (e.g. inactivated influenza vaccines).

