3.6 Rationale for Expanding Inclusion Criteria for Gastric / GEJ Cohort

Recent data provide evidence of clinical activity of anti-PD-L1 therapy in metastatic gastric cancer patients, which supports the expanded inclusion in this trial of subjects who have progressed on first-line chemotherapy for metastatic disease. The evidence includes:

- Data presented at the American Society for Clinical Oncology Annual Meeting 2014 from a Phase I expansion cohort of 16 subjects with gastroesophageal cancer treated with MEDI4736 (anti-PD-L1), which reported 4 out of 16 responders (55).
- Preliminary data from the gastric and GEJ cancer expansion cohort in the current trial (EMR100070-001), which includes 2 unconfirmed PRs out of 6 subjects who have completed 7 weeks of follow-up (as of 17 July 2014).

Based on the above data, eligibility for this cohort will be expanded to allow subjects who have progressed on first-line chemotherapy for metastatic disease to be enrolled, in addition to subjects who have not progressed.

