- Gastric and GEJ cancer, first-line maintenance or second-line:** Histologically confirmed, unresectable locally advanced or metastatic adenocarcinoma of the gastric

and GEJ, treated with first-line chemotherapy combination in metastatic setting with or without disease progression. Subjects should have received no more than 1 line of treatment for metastatic disease. Subjects should not have been treated with trastuzumab (but can be Human Epidermal growth factor Receptor 2 [HER2] positive). Subjects who received any platinum containing doublet or triplet as a neoadjuvant chemotherapy strategy, but are not ultimately candidates for surgery will also be eligible. In addition, subjects with gastric cancer can enter in the study if their WBC is $\geq 2 \times 10^9/L$ with ANC $\geq 1.0 \times 10^9/L$ and lymphocyte count $\geq 0.5 \times 10^9/L$.

- **MBC:** Subjects must have histologically confirmed locally advanced or MBC and have tumor that is refractory to or progressive after standard of care therapy. Subjects must have received no more than 3 prior lines of cytotoxic therapy for metastatic disease. Subjects must have received a taxane and an anthracycline, unless contra-indicated.

Secondary expansion cohorts

- **CRC:** Histologically or cytologically confirmed recurrent or refractory metastatic CRC (according to AJCC/UICC TNM Staging System seventh edition) after failure of prior therapy containing oxaliplatin/fluoropyrimidine and/or irinotecan/fluoropyrimidine and, if eligible, cetuximab (Erbix®) and bevacizumab (Avastin®). These subjects will be enrolled in sites located in the USA only.
- **CRPC:** Histologically or cytologically confirmed asymptomatic metastatic CRPC or minimally symptomatic (according to AJCC/UICC TNM Staging System seventh edition) with objective evidence of disease (non measurable or measurable lesion) with stable, ongoing adequate testosterone suppression proven by castrate levels of testosterone (≤ 50 ng/dL), except for subjects with prior orchiectomy. Minimally symptomatic is defined as patients who do not require consistent treatment with opiates over the last month (less than 7 days of opiates in the last 28 days, and no opiates administered 3 days in a row), for the treatment of their prostate cancer. Additional androgen blockade or treatment with an anti-androgen receptor is acceptable. These subjects will be enrolled in sites located in the USA only.

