- **Urothelial carcinoma:** Histologically or cytologically documented locally advanced or metastatic transitional cell carcinoma of the urothelium (including renal pelvis, ureters, urinary bladder, urethra). A tumor sample (1 tumor block or at least 7 unstained slides) must be available. Subjects can be either: ineligible for cisplatin-based chemotherapy or have progressed after treatment with at least 1 platinum-containing regimen (e.g., platinum plus another agent such as gemcitabine, methotrexate, vinblastine, doxorubicin, etc.) for inoperable locally advanced or metastatic urothelial carcinoma or disease recurrence. Ineligibility to treatment with a platinum salt is defined by the existing of any (at least 1) of impaired renal function, a hearing loss of 25 decibels at 2 contiguous frequencies, or Grade ≥ 2 peripheral neuropathy. Subjects may have received any number of prior systemic therapies for metastatic disease.
- **Renal cell carcinoma, second-line with first-line expansion:** Histologically or cytologically documented RCC with a component of clear cell subtype, with metastasis. A tumor sample (1 tumor block or at least 7 unstained slides) must be available. Eligible subjects must have measurable disease. Subjects must have failed 1 prior systemic first-line regimen for metastatic RCC (except for subjects enrolled in first-line expansion).

Efficacy expansion cohorts:

- **Gastric and GEJ cancer, third line:** Histologically confirmed, unresectable locally advanced or metastatic adenocarcinoma of the gastric and GEJ, treated with both a first-line chemotherapy combination and followed by ramucirumab (alone or in combination). Subjects must have progressed during or after ramucirumab therapy. Subjects with gastric cancer can enter into the study if their WBC is $\geq 2 \times 10^9/L$ with ANC $\geq 1.0 \times 10^9/L$ and lymphocyte count $\geq 0.5 \times 10^9/L$.

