7.2.5 CT or MRI Scans for Tumor Assessment at Baseline

A CT scan or MRI (if MRI is used, CT of chest is mandatory) of the chest, abdomen, and pelvis (at a minimum and other established assessments of tumor burden if CT / MRI imaging is not sufficient for the individual subject; other regions as specifically required for specific tumor indications) will be performed within 18 days prior to trial treatment start in order to document the baseline status of the tumor disease using RECIST 1.1 target and non-target lesions. However, if the results of a CT scan or MRI performed within 4 weeks prior to first treatment are available, the screening CT / MRI does not need to be performed.

A brain CT / MRI scan (either, contrast preferred) is required at screening if not performed within the previous 6 weeks (within 28 days for subjects in the melanoma cohort). In subjects with gastric/GEJ cancer, HNSCC, ovarian cancer, CRPC, mesothelioma, or urothelial carcinoma this scan is only necessary if clinically indicated. Thereafter, brain CT/MRI scan should be done if clinically indicated by development of new specific symptoms.

A bone scan should be done at screening as clinically indicated.

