14.1 Prior Anti-Cancer Therapies/Procedures

The prior anti-cancer treatments and procedures are collected under the Prior Anti-Cancer Drug Therapies Details, Prior Anti-Cancer Radiotherapies Details and Prior Anti-Cancer Surgeries Details eCRF pages.

The overall summary of prior anti-cancer treatments will include: the number and percentages of subjects by type of treatment, i.e.

- Number of subjects with at least one type of prior anti-cancer treatment
- Number of subjects with at least one prior anti-cancer surgery
- Number of subjects with at least one prior anti-cancer drug therapy
- Number of subjects with at least one prior anti-cancer radiotherapy

Summary of prior anti-cancer drug therapy will include the following variables for all the cohorts with exceptions for ovarian cancer cohort:

- Number of subjects with at least one prior anti-cancer drug therapy
- Number of any prior anti-cancer therapy lines: missing/ 1/ 2/ 3/ ≥ 4
- Number of any prior anti-cancer therapy lines as continuous variable
- Number of prior anti-cancer therapy lines for metastatic or locally advanced disease: missing/ 0/ 1/ 2/ 3/ ≥ 4 . If the intent of therapy is metastatic, locally advanced, or palliative, it will be counted into therapy lines for metastatic or locally advanced disease
- Number of prior anti-cancer therapy lines for metastatic or locally advanced disease as continuous variable
- Type of prior anti-cancer therapy: chemotherapy/ antibody therapy/ kinase inhibitors/ hormonal therapy/ vaccines/ bone marrow transplant/ lymphocyte infusion/ other
- Intent of therapy: adjuvant / neo-adjuvant / metastatic / locally advanced / palliative
- Best response: CR/ PR/ PD/ stable disease (SD)/ unknown/ not assessable (NE)/ not applicable. Best response is derived from the last treatment regimen

For secondary ovarian cancer cohort, one additional category will be defined for the following two variables:

- Number of any prior anti-cancer therapy lines: missing/ 1/ 2/ 3/ 4/ ≥ 5
- Number of prior anti-cancer therapy lines for metastatic or locally advanced disease: missing/ 0/ 1/ 2/ 3/ 4/ ≥ 5 .

For the primary gastric and GEJ cancer cohort, the following will be summarized for Not Progressed First Line Cancer (FLC) per drug category:

- Duration of latest prior anti-cancer regimen (Days)
- Duration of latest prior anti-cancer regimen start date to first study treatment (Days)

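### Primary gastric/GEJ cohort, non-progressed stratum: nothing requires the baseline scan to follow the last chemotherapy dose, so shrinkage from that dose can count as an avelumab response

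*Protocol*

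**What the plan says.** **Washout.** Protocol 5.3.2, criterion 3, excludes anticancer treatment in the 28 days before trial treatment, then makes an exception: "Subjects in the gastric and GEJ cohort who have not progressed on first-line chemotherapy may be enrolled within the 28-day period following prior treatment". Side effects of the earlier chemotherapy must have settled to Grade 1 or lower. The exception sets no minimum interval and no condition on the baseline scan.

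**Who this reaches.** The primary gastric/GEJ cohort takes subjects "treated with first-line chemotherapy combination in metastatic setting with or without disease progression" (Protocol 5.3.1). The third-line gastric efficacy cohort does not qualify for the exception: "Subjects must have progressed during or after ramucirumab therapy".

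**Baseline scan.** Under Protocol 7.2.5 the scan "will be performed within 18 days prior to trial treatment start in order to document the baseline status of the tumor disease". No new scan is needed "if the results of a CT scan or MRI performed within 4 weeks prior to first treatment are available". Footnote 9 of the expansion schedule in Appendix I repeats both rules. Neither place has a gastric exception.

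**Analysis.** Protocol 7.3 measures response against baseline tumor burden. Section 11 of the expansion SAP takes baseline as the last observation before first dose and stratifies this cohort by progression status after first-line chemotherapy. SAP 14.1 summarises two quantities for the non-progressed stratum: the duration of the latest prior regimen, and "Duration of latest prior anti-cancer regimen start date to first study treatment (Days".

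**Other statements of the washout.** Protocol 6.5.2 and 7.1.1 restate the 28-day rule without the gastric exception.

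**The concern.** For subjects under the ordinary rule, two limits fit together. No anticancer therapy is allowed in the last 28 days and the scan may be at most 4 weeks old, so the scan follows the last cytoreductive treatment. The exception removes the first limit and leaves the second as it was.

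A non-progressed subject can therefore be scanned, receive a further chemotherapy cycle, and start avelumab with the earlier scan as baseline. These subjects were by definition not progressing on that chemotherapy, so any distortion runs mainly towards apparent response.

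Two outputs are exposed: the response rate of this cohort, and the unconfirmed Week 13 response that drives its 75-subject futility rule (Protocol 8.6; SAP 8.1). That rule counts responses over the whole cohort, not by stratum.

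**Working it through.** **1. Timing, with first dose on Day 1.**
- 4-week waiver: scan on Day -28, chemotherapy on Day -21.
- Ordinary 18-day window: scan on Day -18, chemotherapy on Day -14.

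Both sequences meet the exception in 5.3.2 (if toxicity has settled) and the scan rules in 7.2.5 and footnote 9. The waiver widens the gap but does not create it.

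**2. Does any later rule remove the effect?**
- The SAP definition of baseline does not refer to chemotherapy.
- SAP 16.2 drops assessments made after the start of further anticancer treatment. It does nothing about treatment given before first dose.
- A confirming scan is compared with the same baseline, so confirmation does not help. The futility count uses unconfirmed response in any case.
- Stratifying by progression status isolates the exposed stratum, but not the affected subjects within it.
- From SAP 14.1, time from end of regimen to first dose ≈ (regimen start to first dose) − (regimen duration). Recency is thus roughly derivable, but it is never compared with the scan date.

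**3. Futility rule.** Enrolment stops with 3 or fewer responders in 75. With X ~ Binomial(75, p), P(X ≤ 3) is:

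| True rate p | Computed | Protocol Table 8.2 |
|---|---|---|
| 0.03 | 0.812 | 0.81 |
| 0.05 | 0.480 | 0.48 |
| 0.10 | 0.050 | 0.05 |
| 0.15 | 0.0024 | 0.002 |

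The plan's figures reproduce. If one of the counted responses is spurious, the rule stops only when there are 2 or fewer genuine ones. Keeping 75 as the denominator, which is a slight approximation:
- p = 0.03: P(X ≤ 2) = 0.608, down from 0.812.
- p = 0.05: P(X ≤ 2) = 0.270, down from 0.480.

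At the boundary, 3/75 = 4.0% (stop) becomes 4/75 = 5.3% (continue).

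**4. How many spurious responses?** The documents do not say. The following ranges are assumptions: 25–75% of the 75 subjects non-progressed, 10–30% of those with a cycle after the scan, and 10–20% of those with a carry-over partial response.
- Low: 75 × 0.25 × 0.10 × 0.10 = 0.19.
- High: 75 × 0.75 × 0.30 × 0.20 = 3.4.

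The range runs from essentially none to enough to alter the decision. It cannot serve as an estimate.

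**5. Full cohort.** Protocol 8.1 gives 15/150 = 10% (5.7%, 16.0%), which reproduces by Clopper-Pearson. Three extra responders, again for illustration, would give 18/150 = 12.0% (7.3%, 18.3%).

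**The case against.** The strongest reply is that the matter is small and largely past. The cohort is exploratory: Protocol 8.5.1 reserves confirmatory analysis for the efficacy expansion cohorts. Its analysis is already stratified by progression status. Section 9 of the SAP indicates that the 75-subject gastric cut-off has been reached, and Protocol 3.5.1 speaks of the expansion phase as completed. The SAP says enrolment may be stopped, where the protocol says it will be, and both provide for a comprehensive review afterwards. At a true rate of 10% the stopping probability is only 0.05, so there is little left to distort. Non-progressed subjects include those with stable disease or already in response; that one more cycle would produce a further partial response is an assumption.

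All of this stands, and it limits the weight of the point. It does not supply the missing link between scan date and last chemotherapy dose.

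Four stronger readings are tempting, and the documents do not support them:
- **Early responses were carry-over.** Protocol 3.6 supports wider eligibility with data from this cohort, "which includes 2 unconfirmed PRs out of 6 subjects who have completed 7 weeks of follow-up". It gives no scan or chemotherapy dates for those subjects, does not show that the exception was then in force, and also cites 4 of 16 responders in an external study.
- **The SAP cannot show how recent the chemotherapy was.** It can, roughly, from the two quantities in 14.1.
- **The 4-week waiver alone is at fault.** The 18-day window has the same gap.
- **The tests of response rate above 10% are compromised.** They belong to the efficacy cohorts, and the only gastric cohort among these requires progression.

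**Conclusion.** The point holds as a gap in the written rules. In the non-progressed stratum of the primary gastric/GEJ cohort, chemotherapy may be given after the baseline scan, and no analysis rule identifies or sets aside responses measured against such a scan. This follows from the text and needs no assumption.

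The size of any bias is unknown. It depends on the number of subjects with a cycle after the scan and on the carry-over response rate, and the documents give neither. The fall in stopping probability (0.81 to 0.61 at a true 3%, 0.48 to 0.27 at 5%) shows how sensitive the rule is to a single misattributed response. It does not show that one occurred or that a decision changed.

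The point deserves correction because results under this SAP go into study reports and regulatory submissions (SAP Section 5) and the remedy is cheap. No confirmatory conclusion depends on it.

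**What to change.** **Protocol, for any further enrolment.** In 7.2.5 and in footnote 9 of the expansion schedule, state that for gastric/GEJ subjects enrolled under the 28-day exception the baseline CT or MRI must post-date the last prior chemotherapy dose, whether it is taken in the 18-day window or accepted under the 4-week waiver. Reconcile 6.5.2 and 7.1.1 with criterion 3 of 5.3.2. No view is taken here on the length of the washout.

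**SAP 14.1 and 16.2.**
- Derive, for each subject, the order of the last prior-chemotherapy date and the baseline scan date.
- Report response with and without subjects whose scan came first: overall, in the non-progressed stratum, and retrospectively for the 75-subject interim.
- SAP 18.2 imputes a missing day of prior therapy to the first of the month, which tends to place chemotherapy before the scan and hide exposure. Treat subjects whose order depends on an imputed day as possibly exposed.

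A delayed effect of chemotherapy given before a compliant scan would remain, so the non-progressed stratum should still be reported separately.

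**Cost.** A few subjects would need a new screening scan, and the stratum response rate may fall slightly. The SAP change is one derived variable and a few tables; the sponsor should confirm that both dates are in the database.

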5.4 Criteria for Initiation of Treatment with the Investigational Medicinal Product

The inclusion and exclusion criteria will be checked at the screening visit. Eligible subjects will be enrolled before treatment start after verification of fulfilling all inclusion criteria without matching any exclusion criterion.

5.5 Criteria for Subject Withdrawal

5.5.1 Withdrawal From the Trial

Subjects are free to discontinue the trial at any time without giving their reasons.

A subject must be withdrawn in the event of any of the following:

- Withdrawal of the subject's consent.
- Participation in any other therapeutic trial during the treatment duration of this trial.

If a subject has failed to attend scheduled trial assessments, the investigator must determine the reasons and the circumstances as completely and accurately as possible.

In case of premature withdrawal from the trial, the investigations scheduled for the last visit should be performed (see Section 7.1.3 for end-of-treatment visit), if possible, with focus on the most relevant assessments. In any case, the appropriate case report form (CRF) section must be completed.

In the dose escalation part of the trial, only subjects who do not complete the DLT observation period (3 weeks) for reasons other than a DLT will be replaced. Subjects who require discontinuation of avelumab due to a DLT will not be replaced. In the expansion part of the trial, if a subject is withdrawn prior to progression for any reason, they will not be replaced except for the rule described above.

